- Systematic review of charts from primary care and endocrinology clinics with previous approval from the different providers.
- Advertisement in social media outlets, local radio and TV stations.
- Submission a search request to the VA data warehouse (VINCI) for a listing of patients at the Harry S. Truman VA who have a diagnosis of T2D and are within the targeted age range and fulfil inclusion/exclusion criteria.

Screening Procedures:

Interested participants will be instructed, via letters, flyers, or via VA patient portal to contact study coordinator for a 10-minute interview (using a waiver of documentation of consent approved by the local IRB). The interview will be conducted with the goal of determining eligibility (demographics, height, weight, current medical illnesses/ medical history, and use of medications will be obtained). If a subject expresses interest to participate in the study, a screening visit will be scheduled.

Participant Compensation:

We have completed multiple clinical studies involving human subjects with adherence rates of greater than 95% and subject retention rates of greater than 85%. We utilize a validated retention strategy published by Jeffrey et al (Am J Clin Nutr. 2003;78(4):684-689) that has been successful. With respect to subject honoraria, subjects will be paid \$25 after completion of the screening visit, \$75 after the baseline visit, and \$255 after the final visit. Subjects will also receive travel compensation of \$0.41/mile

traveled (round trip) from their residence to the Harry S. Truman VA Hospital and Clinics for each of their study visits. If subjects are asked to repeat safety labs, you will be compensated for applicable travel at a rate of \$0.41/mile traveled (round trip) from their residence to the Harry S. Truman VA Hospital and Clinics. Thus, a total compensation of \$355 plus applicable travel compensation will be provided as study events are completed. Participants will receive study compensation via check.

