Insulin and glucose infusion with leg blood flow, sphygmomanometry, and beat- to-beat via finometer			X				X
Contrast enhanced ultrasound			X				X
DEXA			X				X
Supplement/placebo dispensing			X				
Daily Supplement/Placebo dosing					X		
Weekly phone check-in					X		

Table 1. Schedule of study activities. Note that after screening visit, once eligibility has been confirmed subject will be randomized.

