5.6 Data Analysis

For Aim 1 of the study, twenty-four subjects (**n=24**) will be enrolled in the DSGP/placebo treatment with 12 subjects randomized to each group. For Aim 2 of the study, seventy-two subjects (**n=72**) will be enrolled with eighteen subjects randomized to each of the four interventions.

Statistical analysis, sample size and power calculations:

Aim 1: We will analyze change in PBR (and change in other secondary outcomes) using ANCOVA with baseline PBR as a covariate and dietary supplement as a main effect. We will use residual diagnostic plots to check for violations of assumptions on normality and equal variance among groups. If variance is not equal, separate variance components can be estimated in SAS mixed procedure to account for these differences. Inspection of the variance estimates and a likelihood ratio test can validate the need for this approach. Transformation may be used to correct for skewness and unequal variance. This analysis has two treatment levels to contrast and no need for multiple contrast correction like Bonferroni.

Power estimates are based on preliminary data in PBR (for Aim 1) and FMD (for Aim 2). We observed a mean of 1.742 (standard deviation, SD=0.27) and 1.45 (SD=0.20) in PBR for type 2 diabetes (T2D) and healthy subjects, respectively. Based on our findings in the pre-clinical mouse model of T2D that glycocalyx thickness was completely restored with DSGP, we predict that DSGP in T2D subjects will cause a mean decrease in PBR of 0.3, with no changes in response to placebo. As presented in Figure 3E, we observed a mean of 3.78 (SD=1.86) and 7.06 (SD=2.21) in FMD for T2D and healthy subjects, respectively. We predict that DSGP + exercise will cause a mean increase in FMD of 2, which represents two-thirds of the distance between healthy and T2D subjects. Our pilot data was also

used to estimate the within-subject variance, assuming a correlation of $r=0.6$ between serial measurements on the same subject.

For Aim 1, assuming pre-treatment PBR $SD=0.27$, post $SD=0.20$, and correlation between pre and post is 0.6 , then the SD of the pre to post treatment change in PBR is 0.22 . A sample size of $n=10$ per group will provide 82% power when the true mean difference in PBR change is 0.3 . Adjustment of sample size for 20% attrition results in 24 subjects (12 per group) for Aim 1 and 72 subjects (18 per group) for Aim 2.

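### Aim 1: randomizing 12 per group keeps the 10 completers behind the 82% power only up to 16.7% attrition, not the stated 20%; at 20% loss, change-score power is about 80%

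*Combined protocol and SAP*

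**What the plan says.** All the figures for Aim 1 are in section 5.6 of the combined protocol and SAP.

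- **Power.** Ten "per group will provide 82% power when the true mean difference in PBR change is" 0.3. The inputs are a pre-treatment SD of 0.27, a post-treatment SD of 0.20 and a pre-post correlation of 0.6, from which the plan takes the SD of change as 0.22. It states neither alpha nor sidedness.
- **Attrition.** The next sentence reads: "Adjustment of sample size for 20% attrition results in 24 subjects (12 per group) for Aim 1". No inflation formula is given.
- **What the 12 counts.** The opening of section 5.6 says that the 24 subjects "will be enrolled in the DSGP/placebo treatment with 12 subjects randomized to each group". The note to Table 1 (section 5.4) places randomization after screening: "once eligibility has been confirmed subject will be randomized". So 12 is the number randomized per group, before any loss on study.
- **Planned analysis.** "We will analyze change in PBR (and change in other secondary outcomes) using ANCOVA with baseline PBR as a covariate".
- **Retention.** Section 5.2 reports that the team's past studies retained more than 85% of subjects.

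Section 5.7 on withdrawal has no rule for replacing subjects who drop out after randomization, and none appears elsewhere.

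**The concern.** An allowance for attrition should leave the number of completers on which the power was computed. Here 10 per group gives 82%, the assumed loss is 20%, and the number randomized is 12 per group. A 20% loss from 12 does not leave 10.

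The power statement and the attrition statement are adjacent, so the natural reading is that 82% still holds after a fifth of the subjects are lost. The IRB and the Data Monitoring Committee, which follows accrual and retention, would read it that way. If the plan's own calculation does not support this, either the attrition allowance or the power is overstated.

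**Working it through.** **1. Reproduce the plan's 82%.**

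SD of change = √(0.27² + 0.20² − 2 × 0.6 × 0.27 × 0.20) = √(0.0729 + 0.0400 − 0.0648) = √0.0481 = 0.2193. The plan rounds this to 0.22.

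For a two-sample t-test on change scores with 10 per group, the noncentrality is 0.3 / (0.22 × √(2/10)) = 3.05 on 18 degrees of freedom. At two-sided 0.05 the power is 82.2% (82.4% with the unrounded SD), which matches the plan. A one-sided t-test gives 90.1% and a two-sided normal approximation 86.2%; neither matches. Two-sided 0.05 is therefore an assumption, adopted because it reproduces the stated figure.

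**2. Check the attrition step.** This needs no assumption about alpha, test or variance.

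- Completers at 20% loss: 12 × 0.8 = 9.6 per group; 24 × 0.8 = 19.2 in total.
- Number needed to keep 10: 10/0.8 = 12.5 per group, or 13 in whole subjects (26 in total).
- Largest loss from 12 that leaves 10: 2/12 = 16.7%.

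**3. Where the 12 may come from.** Three routes give it:

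- 10 × 1.2 = 12, multiplying by 1.2 instead of dividing by 0.8;
- 12.5 rounded down;
- an unstated 80% power target, which needs about 9.5 per group, and 9.5/0.8 = 11.9.

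The documents do not say which was used. The result in step 2 is the same for all three.

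**4. Change-score power after loss** (difference 0.3, two-sided 0.05). Each range runs from SD 0.22 to SD 0.2193.

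| Completers | Power |
|---|---|
| 10 + 10 | 82.2–82.4% |
| 9.6 per group (20% loss) | 80.4–80.7% |
| 10 + 9 (19 completers) | 79.9–80.1% |
| 12 + 12 randomized, each subject lost independently with probability 20%, averaged | 79.5–79.8% |
| Same, with probability 15% | 82.4–82.6% |

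**5. The planned ANCOVA.** The residual SD is the post-treatment SD × √(1 − 0.6²), that is, × 0.8. At 10 + 9 completers there are 16 degrees of freedom.

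- Post SD 0.20 in both arms: residual SD 0.16, power 97%.
- Post SD 0.27 in both arms (assumption): residual SD 0.216, power 81%.

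**6. Past retention.** At 85%, 12 × 0.85 = 10.2 per group and 24 × 0.85 = 20.4 in total, so on average 10 per group would remain.

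**The case against.** The strongest objection is that this hardly matters. The gap is 0.4 subject per group and about 2 points of power, and power at the assumed loss is still about 80%. That is accepted. It limits the point to a correction of wording.

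Second, the plan never says outright that 82% survives a 20% loss. In whole subjects, losing 2 of 12 leaves exactly 10, and 12 would be a correct allowance for an 80% target. But no such target is stated, and the attrition sentence directly follows the 82% at 10 per group. If 80% was meant, saying so is one of the two corrections below.

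Third, the analysis will be ANCOVA, whose power at 19 completers could be anywhere from 81% to 97% under the two variance assumptions tried. That spread exceeds the attrition effect. The 81% is also not like for like, since a post SD of 0.27 gives an SD of change of √(2 × 0.27² × 0.4) = 0.24 rather than 0.22. This tempers any worry about the trial's real power, but the plan justifies its size by the change-score figure, and the completer count is wrong under any analysis.

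Fourth, the 16.7% threshold assumes equal losses in the two arms. Four losses from 24 could leave 11 + 9 (81.8–82.1% power) or 12 + 8 (80.7–80.9%). With independent dropout at 15%, both arms keep at least 10 only 54% of the time. This stands as a caution on wording and does not affect the 20% result.

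Finally, section 5.2 foresees about 200 consented subjects. That number serves both aims, is given as what is needed to reach 24 and 72, and reads as screening overage. It does not provide for replacement after randomization.

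**Conclusion.** The concern holds. Twelve randomized per group does not leave 10 completers at 20% attrition; it does so only up to 16.7%, with losses equal between arms. That much is arithmetic on the plan's own numbers.

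By the plan's change-score calculation, power at 20% loss is about 80% rather than 82%. This rests on two-sided 0.05, which the plan does not state, and on the plan's difference, SDs and correlation. The planned ANCOVA may have more power. The cause of the 12 cannot be established from the documents. The effect is small, the design need not change, and nothing is claimed about Aim 2, for which no number before attrition is given.

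**What to change.** Keep 24 subjects and correct the Aim 1 part of the attrition sentence in one of two ways.

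1. State that 12 per group leaves 10 completers per group for attrition up to 16.7%, if losses are equal between arms. This is consistent with the past retention above 85% in section 5.2, but it lowers the stated allowance from 20%.
2. Keep 20% attrition and state that about 19 completers are then expected, with about 80% power by the change-score calculation. This needs no condition on how losses split between arms beyond near balance, and it leaves the attrition assumption as planned, so it is the cleaner choice.

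Whichever is chosen, add the alpha and sidedness used. The cost is one sentence, with no extra subjects and no change to the design.

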5.7 Withdrawal of Subjects

Subjects may be withdrawn from the study at the discretion of the investigator due to a safety concern or if judged non-compliant with trial procedures.

A subject must be withdrawn from treatment if one of the following applies:

- Subject chooses to withdraw from the study at any time
- Pregnancy or intention of becoming pregnant during study duration
- Serious adverse effect occurs
- If a significant violation of the protocol occurs, as defined by the sponsor and the coordinating investigator
- Other circumstances that would endanger the health of the subject if he/she were to continue his/her participation in the trial

Whenever an investigator terminates a subject's participation in research, the investigator must explain to the participant the reasons for the termination and, as appropriate, other treatment options available to the participant.

The PIs will note the number of and summarize the reasons for early withdrawals.

Should a subject withdraw consent to participate in the study, he/she may either:

- Agree to continue releasing information for the study
- Refuse to allow further release of information.

If any subject refuses to return for the defined assessments or is unable to do so, every effort should be made to contact him/her or a knowledgeable informant by telephone. Attempts to contact the subject should be documented in the subject's records. If any subject refuses to be contacted by telephone (e.g. the subject withdrew consent to release further information), every effort should be made to obtain vital status (alive or dead) information through consultation of public databases, wherever allowed by local regulations.

6.0 Reporting

Plan for reporting study deviations

Any minor problem/deviation will be summarized and reported to the IRB within five working days of awareness, including any event that does not: 1) increase the risk to the subject, 2) decrease the benefit to the subject, or 3) significantly affect integrity of the research data. Any major problem/deviation will be summarized and reported to the IRB within five working days of awareness, including any event that: 1) increases the risk to the subject, or 2) significantly affects integrity of the research data.

Stopping rules

We will stop an individual study if a serious adverse event occurs. If four or more subjects experience a serious adverse event requiring termination of the study, the study will be stopped and the events will be discussed with the IRB to determine whether it is appropriate to continue and/or determine appropriate modifications to the protocol to avoid further adverse events. All unanticipated serious adverse events will be submitted for review according to current protocols. The medication will be discontinued at the discretion of the study safety officer.

Definition of serious adverse event (SAE)

A SAE is classified as any untoward medical occurrence that, at any dose, meets any of the following criteria (a – f):

- a. Results in death
- b. Is life-threatening

The term 'life-threatening' in the definition refers to an event in which the subject was at risk of death at the time of the event, it does not refer to an event which hypothetically might have caused death if it were more severe.

- c. Requires inpatient hospitalization or prolongation of existing hospitalization

A hospitalization or prolongation of hospitalization will not be regarded as a serious adverse event if at least one of the following exceptions is met:

- The admission results in a hospital stay of less than 12 hours
- The admission is pre-planned
- The admission is not associated with an adverse event related to the study medication or study procedures as determined by the study safety officer and data safety monitoring board.

- d. Results in persistent or significant disability / incapacity

Disability means a substantial disruption of a person's ability to conduct normal life's functions.

- e. Is a congenital anomaly / birth defect

- f. Is another serious or important medical event as judged by the investigator.

The data safety monitoring plan (DSMP) for this study is focused on the supervision performed by the PIs, the Co-Investigator, [name], and the safety officer, [name]. Monitoring will include enrollment, attrition, efficacy end-points, and adverse events.

Data Safety Monitoring Plan

Data and safety monitoring for this study will be provided by the Clinical Science Research & Development (CSR&D) centralized Data Monitoring Committee (DMC). The DMC is provided by CSR&D to ensure independent oversight of the safety and integrity of the project. The DMC is an independent multidisciplinary group, whose members have collectively – through research, education, training, experience, and expertise – the requisite knowledge pertinent to the subject areas to be reviewed. Membership details are available on the CSR&D website. The DMC will provide an ongoing independent evaluation of this study focused on safety and feasibility, including participant accrual and retention, adverse events monitoring, and data analyses. Meetings will be held two times per year at which time recommendations will be made to the Director of CSR&D for endorsement. These recommendations will range from approval to continue (unconditionally or with conditions to be addressed) to probation or possibly termination if there are problems with enrollment or safety concerns.

Process for managing and reporting adverse events, serious adverse events and unanticipated problems. Unanticipated events will be reported to IRB, and both serious and non-serious adverse events will be reported to the DMC. For reporting to the DMC, adverse events will be categorized and classified according to Common Terminology Criteria for Adverse Events Scale (CTCAE v6.0). Safety reports will be sent to the safety officer. The PIs will be responsible for assembling the data and producing these reports, as well as assuring that all parties obtain copies of these reports.

Qualifications and responsibilities of the Safety Officer. The safety officer for this trial will be [name]. He is the Associate Chief of Staff for Research and Development and the Research Integrity Officer at the Harry S Truman VA Hospital. In addition, [name] is Professor in the Division of Nephrology at the University of Missouri and a clinician scientist. As Safety Officer, [name] will review eligibility criteria with [name], and be unblinded as to treatment assignment (if needed). He will review all reports sent by the study coordinator to determine whether there is any corrective action, trigger of an ad hoc review, or stopping rule violation that should be communicated to the VA Research and Development Committee, the IRB and the DSMC. In addition, the safety officer may comment on whether the study investigator needs to report any specific out-of-range laboratory data.

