3.0 Objectives

Our overarching hypothesis is that endothelial glycocalyx degradation is a key factor that precludes shear stress mechanotransduction and consequent exercise-induced vascular adaptations in T2D. (Figure 1). A corollary to this hypothesis is that restoration of the endothelial glycocalyx by DSGP will improve vascular adaptations to exercise in T2D.

Specific aims are as follows:

Aim 1 (Proof of Concept Clinical Trial Phase): Document that DSGP enhances endothelial glycocalyx integrity in Veterans with T2D. Although we provide preliminary evidence that DSGP can increase glycocalyx thickness and endothelial function in a mouse model of T2D, this will be the first study to demonstrate these effects in T2D subjects. The effects of DSGP for eight weeks on glycocalyx integrity and endothelial function will be studied using a double-blinded randomized placebo control trial.

Aim 2 (Expanded Clinical Trial Phase): Demonstrate the permissive role of the endothelial glycocalyx for exercise-induced vascular adaptations in Veterans with T2D. Having shown that endothelial glycocalyx restoration via DSGP in T2D subjects is feasible, we will now investigate whether such supplementation potentiates exercise training-induced improvements in endothelial function. This will be accomplished with a factorial balanced design in which T2D subjects will be randomized to DSGP or placebo with and without concurrent exercise training for eight weeks.

RELEVANCE TO VETERANS AND THE VA: Targeting the glycocalyx holds extraordinary promise for achieving optimal exercise-induced vascular adaptations in T2D, thus maximizing the cardiovascular benefits of exercise.

[figure not shown]

Figure 1. Overarching hypothesis: Endothelial glycocalyx degradation (left side) is a key factor precluding shear stress mechanotransduction (i.e., it renders the endothelium unable to detect shear stress forces) that makes T2D individuals exhibit diminished exercise-induced vascular adaptations. Restoration of the glycocalyx (right side) reinstates shear stress echanotransduction, permitting optimal exercise-induced vascular adaptations.

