DEXA and anthropometrics: Radiation exposure during DEXA is equivalent to about 2% of the average radiation dose from all sources (natural background radiation, consumer appliances, radon gas, medical tests, etc.) that a person in the United States receives each year. Subjects who participated in any other research study or medical procedure involving significant ionizing radiation exposure (e.g., multiple chest x-rays) in the past 12 months will be excluded. Only postmenopausal subjects will be included in the study; therefore no pregnancy test will be pursued. Body weight is measured to the nearest 0.1 kg and height to the nearest 0.1 cm. This procedure is not standard of care.

Dietary Recall/Assessment: The study dietitian or a trained research technician will interview research subjects about the foods and beverages that they have recently consumed or asked them to keep a record of the foods that you consume for 3 days. There are no risks with this procedure. Dietary Recall/Assessment will be performed at the preassessment and post assessment visits.

Supplement, Endocalyx: The Dietary Supplementation of Glycocalyx Precursors (DSGP) commercially available as Endocalyx™ (Microvascular Health Solutions LLC, Alpine, UT) which includes: glucosamine sulfate, fucoidan, superoxide dismutase, and high molecular weight hyaluronan is the supplement being compared to placebo in this study. In addition, we will monitor coagulation tests (PT and PTT) at baseline, 7-14 days (this blood check will occur at VA main hospital) and during final visit. There are no known risks associated with supplementation with DSGP. Nevertheless, subjects with known allergies to any of the compounds in the supplement (glucosamine extract, fucoidan extract, olive extract, artichoke extract, red and white grapes extract, melon concentrate, hyaluronic acid) will not be included in the study. If subjects exhibit changes in their health status across any system related or unrelated to the study intervention, [name] (safety officer) will be consulted for advice. Study subjects will be responsible for taking the study supplement or placebo at home, daily for the span of 2 months. The study team will monitor dosing compliance weekly. The use of Endocalyx in this study is filed under the research IND 164629 that was submitted on 11/23/2022.

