Randomization and Blinding: Subjects will either take a placebo or a supplement as part of this study. There is an equal but random chance that a subject will be assigned to either the placebo or

supplement treatment. The study team will be blinded to the study treatment. There is no risk associated with randomization or blinding in this study.

Heart rate measurements via ECG: Heart rate will be measured. Some people may have a skin irritation from the patches that connect the wires on your chest to the computer. Skin and hair are pulled slightly when the patches are removed after the test. Research personnel will attach and remove the patches as carefully as possible. Heart rate monitoring will occur at screening, preassessment, and post assessment visits.

Insertion of venous catheters: IVs will be placed to collect blood during study assessments. The potential risks of venous catheterization include infection, swelling and discomfort at the catheter insertion sites. Some bleeding may occur during the insertion of the catheters as well after the catheters have been removed. There is also the possibility of fainting, dizziness, and possible pain and bruising as a result of catheter insertion. These risks will be greatly minimized by using sterile procedures and having an experienced registered nurse placing the venous catheters. Insertion of IVs will occur at preassessment and post assessment.

Medication hold the morning of the study visits: Subjects will be instructed to hold diabetes medications the morning of the CTSU visit to minimize the risk of hypoglycemia. These medications include: insulin, sulfonylureas, gliptins, metformin, acarbose, GLP-1 analogs, inhibitors of the sodium glucose co-transporters. [name] will review medications ahead of the visit and instruct subject which medications to hold.

Transport via wheelchair: If research procedures are completed in both CTSU locations during the same visit, participants will be transported via wheelchair between locations. Wheelchair transport will minimize the physical strain on research participants as well as reduce the vascular impact of ambulating during a study visit. Study staff assisting in wheelchair transportation will be trained on common safety practices to minimize risk of injury and/or fall to the participants and themselves.

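### An admission judged unrelated drops out of SAE criterion (c), so the SAE count is partly filtered by a causality opinion (minor)

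*Combined protocol and SAP*

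**What the plan says.** The definition in section 6.0 opens with outcome: "A SAE is classified as any untoward medical occurrence that, at any dose, meets any of the following criteria". Six criteria follow, and nothing in that opening refers to cause.

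Criterion (c) covers inpatient admission or a prolonged stay. It then states that such an event "will not be regarded as a serious adverse event if at least one of the following exceptions is met". There are three exceptions: a stay shorter than 12 hours, a planned admission, and an admission that is not linked to an event "related to the study medication or study procedures as determined by the study safety officer and data safety monitoring board". The last is decided jointly by those two parties.

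Three other places bear on the point:

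- **Section 6.0, Stopping rules.** One SAE stops the individual's participation. A second rule counts four or more subjects with an SAE, and adds the condition that the event requires termination of the study.
- **Section 5.7, Withdrawal of Subjects.** Withdrawal from treatment is mandatory after a *serious adverse effect*, a term that is not defined.
- **Section 6.0, Data Safety Monitoring Plan.** Serious and non-serious adverse events both go to the DMC, categorised under CTCAE. Unanticipated events go to the IRB.

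**The concern.** Seriousness and relatedness answer different questions. Seriousness describes what happened to the subject; relatedness is a view on why. When the second decides the first, the SAE count no longer shows how many subjects had a serious outcome. It shows how many had one that the assessors did not attribute to something else.

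An all-cause SAE count lets someone outside the assessment see a pattern that nobody attributed to the supplement case by case. If admissions judged unrelated have already left the category, that count cannot be recovered from the SAE listing alone. What is at stake is the meaning of the safety summary. The efficacy result is not involved.

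**Working it through.** The plan states no figure on this point, so there is nothing to reproduce. The check is a reading of the text.

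**Step 1: is one exception enough?** Yes. The lead-in asks for at least one of the three. A joint finding of unrelated is therefore sufficient by itself, however long and however unplanned the stay.

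**Step 2: is the causal condition found elsewhere in the definition?** No.

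- Criteria with a relatedness condition: 1 of 6, namely (c).
- Exceptions to (c) that rest on a view of cause: 1 of 3. The other two, length of stay and prior planning, are matters of fact.
- Criterion (f) also rests on judgment, but that judgment concerns the importance of the event and not its cause.

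**Step 3: does another route bring the admission back?** Sometimes. I read the exceptions as limiting (c) alone, which is the reading more favourable to the plan; the wording does not say so expressly. On that reading an unrelated admission is still an SAE if it ends in death, is life-threatening, leaves significant disability, or is judged serious or important by the investigator. No other section restores the remaining admissions.

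**Step 4: compare two identical admissions.** Take two unplanned stays of 12 hours or more, neither meeting (a), (b), (d) or (f).

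| | Judged related | Judged unrelated |
|---|---|---|
| Outcome | Hospitalised | Hospitalised |
| Status under (c) | SAE | Not an SAE |
| Reaches the DMC as | Serious event | Non-serious event |

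The outcome is the same and only the opinion differs. That is the whole of the defect.

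**Step 5: how many subjects?** The expected number in Aim 1 would be 24 × p × u. Here p is the risk of admission over the eight weeks, and u is the share of those admissions that meet all the conditions in Step 4 and are judged unrelated. The 24 comes from section 5.6. The documents give neither p nor u, so no estimate follows.

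**Step 6: what else uses the label?** The individual stop uses SAE status directly. The four-subject rule uses it with a further condition. The withdrawal rule in section 5.7 appears to use it under a different name. A change to the definition therefore reaches beyond the safety tables.

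**The case against.** The strongest reply is that this is a labelling choice, openly written into the definition, and that no information is shown to be lost. Most of that stands. The exceptions are part of the definition, so the text does not contradict itself. The decision is joint, which makes a careless exclusion less likely. Until it is made, the natural reading is that the admission remains an SAE. Section 5.5 sends health changes, related or not, to the safety officer. The reply does not remove the point that the SAE count, as defined, depends on attribution.

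Several stronger readings are tempting, and the documents do not support them:

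- **Unrelated admissions disappear from oversight.** They do not, since non-serious events also go to the DMC.
- **The assessors have almost nothing on which to judge cause.** Section 5.5 does say of the supplement: "There are no known risks associated with supplementation with DSGP". But it also sets out risks for phlebotomy, catheters, the insulin infusion and the contrast agent, and provides for PT, PTT and safety laboratory tests. The remark in section 3.0 that "this will be the first study to demonstrate these effects in T2D subjects" concerns glycocalyx thickness and endothelial function; it is not a statement about safety evidence.
- **Unblinding could colour the relatedness decision.** Section 6.0 lets the safety officer be unblinded if needed. Nothing says that this is done for, or before, a relatedness decision, so the inference rests on silence.
- **One or two subjects would be relabelled.** With p from 2% to 10% and u from 50% to 90%, the formula gives 24 × 0.02 × 0.50 = 0.24 to 24 × 0.10 × 0.90 = 2.16. Both inputs are unsourced assumptions, so the range is not evidence of size.
- **The four-subject rule is disabled.** The documents give no event rate, and that rule has a further condition. Its behaviour cannot be worked out from the text.

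**Conclusion.** The point holds and is minor. For admissions outside (a), (b), (d) and (f), and outside the two factual exceptions, criterion (c) makes seriousness depend on a causality opinion. The SAE count is to that extent filtered by relatedness.

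This rests on the wording alone and needs no assumption about rates. It does assume that the exceptions limit (c) only. If they were read as removing an admission from SAE status altogether, more events would be affected. The number of subjects cannot be estimated from the documents. No difference between arms follows, and the ANCOVA of change in PBR is unaffected.

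**What to change.** For classification and reporting only:

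1. Base seriousness under (c) on outcome, by taking the relatedness exception out of the definition. The two factual exceptions are not at issue here.
2. Record relatedness as a separate field for every adverse event.
3. Report two counts to the DMC: all-cause SAEs and related SAEs.

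The cost is a change of wording in section 6.0, one case-report-form field and one additional count in the DMC report. The downside is that a few more events will carry the SAE label.

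That downside has a consequence. The individual stop is tied to SAE status, so changing the label alone would also widen that trigger. The sponsor must therefore reconcile three places with the revised definition in the same amendment: Stopping rules and the Data Safety Monitoring Plan in section 6.0, and Withdrawal of Subjects in section 5.7, including its undefined term. The oversight body, called a data safety monitoring board, a DMC and a DSMC in different parts of section 6.0, should be given one name at the same time. What the stopping and withdrawal rules should be is for the sponsor; none is proposed here.
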